6.4 Missing Data

In addition, the means and ranges of all variable distributions and outlying data or improbable combinations of variables will be examined before analysis is undertaken.

Endpoint analysis will be performed with and without using imputation of missing data (where applicable) to estimate the effect of missing data on the ITT and PP population. Differences between their results will be summarized and discussed.

6.5 Interim Analyses and Data Monitoring

No interim analysis is planned.

The data will be monitored according to the Monitoring Plan through central and remote monitoring strategies. Outlier data will be queried and remote access to electronic medical records (EMR) may be requested for source data verification (SDV).

Each clinical site will be monitored according to the study monitoring plan to ensure to verify that:

- The rights and well-being of the participants are protected
- The reported study data are accurate, complete and verifiable from source documents
- The conduct of the study is in compliance with the currently approved Clinical Investigation Plan (CIP)/ amendment(s), Good Clinical Practice (ISO 14155), and applicable requirements of the research ethics board (REB)
- There is adequate participant enrollment

6.5.1 Stopping Rules

N/A

6.5.2 Analysis Methods to Minimize Bias

Endpoint data between sites will be assessed and compared to ensure there is no site-specific bias.

7 Summary of Study Data

Descriptive statistics will be generated for all endpoints using a 1-sided 95% confidence interval. Participant data will be quantified. For quantitative parameters, descriptive statistics will be reported: number, mean, standard deviation (SD), minimum, median and maximum values.

For categorical variables, frequency and percentage will be reported. The primary endpoint will be compared to historical data using one-way analysis of variance.

7.1 Variable Assessment

Variable	CRF and data point
Inclusion	Inclusion CRF_Reflector Location
Per protocol completion	Surgery CRF_Type of surgery
Intention to treat completion	Study Completion CRF_Reason for completion
Device insertion success	Inclusion CRF_Deployment within lesion
Device retrieval success	Surgery CRF_Reflector retrieval success
Procedural success	Outcomes CRF_Margin assessment
Efficiency endpoint	Additional visit CRF_Number of visits
Device Safety	Adverse Event CRF_Device Related

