#### 3.2 SCOUT® Reflector

The SCOUT® Reflector is delivered via a delivery system to a pre-determined site in close proximity or within the identified tissue lesion. The Reflector is designed to be highly reflective to radio frequency (electromagnetic wave/micro- impulse radar) signals allowing it to be easily identified and located within soft tissue by the electromagnetic wave signal. The Reflector is delivered percutaneously. The SCOUT® Reflector is preloaded into either the SCOUT® Delivery Device or SCOUT® Bx Delivery Device. The standard SCOUT® Delivery Device contains a 16G introducer needle which retracts into the handle when a release button is actuated, thereby deploying the SCOUT® Reflector. The SCOUT® Bx Delivery Device consists of a plastic molded handle and a 15G rigid cannula, and it is designed for insertion through the biopsy introducer sheath utilized with the following biopsy devices (Hologic Eviva 0913-20; 1213-20 (STX), Hologic BREV09 (STX), ATEC ILS 0914-20 (MRI)). The SCOUT® Reflector is deployed by actuating a

deployment plunger. Availability of these different delivery device configurations within this post-market registry study is dependent upon regional regulatory licensing/clearance. The SCOUT® Reflector and delivery systems are provided as sterile single-use devices.

Part no.	Description
SSR05-01	SCOUT® 5cm Delivery Needle and Reflector
SSR75-01	SCOUT® 7.5cm Delivery Needle and Reflector
SSR75S-01	SCOUT® 7.5cm Delivery Needle and Reflector, Single-handed
SSR75SM-01	SCOUT® 7.5cm Delivery Needle and MINI Reflector, Single-handed
SSR10-01	SCOUT® 10cm Delivery Needle and Reflector
SSR13B-01	SCOUT® Bx Delivery System

TABLE 1: LISTING OF SCOUT® REFLECTOR AND DELIVERY SYSTEM MODELS

All future models that are regulatory licensed/cleared for the same indication in the region of the participating site will be allowed in this registry. Note: Please refer to the Instructions for Use of the device for complete information.

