#### 4.7 Device Period

Insertion of the SCOUT® Reflector shall be conducted according to the IFU at the time of biopsy. The physician will follow regular clinical practice before and during the biopsy procedure.

SCOUT® Reflector may be inserted in a soft tissue biopsy site or a soft tissue site intended for surgical removal as per IFU and clinician decision. Additionally, as per clinician decision, more than one (1) SCOUT® Reflector may be inserted in a participant (bracketing) ensuring a minimum distance of 25 mm between Reflectors.

The data collected during the biopsy and reflector insertion will consist of the following:

- Patient demographic: age, weight, height and diagnosis
- Date of assessment
- Date of biopsy and insertion
- Reflector insertion data: success, deployment within lesion or distance from lesion, depth of reflector, type of guidance used, number of reflectors used, type of lesion
- Lot number(s) and model of the SCOUT® Reflector

- Reflector detection (if performed)
- Adverse events (if applicable)

The data collected during the surgery will consist of the following:

- Date of surgery
- Neoadjuvant therapy (if applicable): start and stop date
- Reflector detection: success before or after incision
- Reflector retrieval data: success, identification and retrieval duration
- Operative time: Time from beginning the detection to the time the lesion is removed from the breast.
- Participant satisfaction questionnaire: this may be completed by/collected from the participant up to 2 weeks after the surgery.
- Adverse events (if applicable)

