3.2 Endpoints

Primary Endpoint: The number of patient visits to the breast center for invasive procedures from the time of biopsy to surgery.

Secondary Endpoint:

1. Device success: percent successful localization, detection and retrieval;
2. Device safety: rate of device-related adverse events;
3. Procedural success: absence of close margins (DCIS: <2mm), positive margins (tumor on ink) or requirement for re-excision.
4. Duration (days) from assessment to surgery and biopsy to surgery;
5. Radiologist assessment: ease of placement; ability to position reflector in desired location; scheduling flexibility; visibility on ultrasound/ mammography (immediate and late); artifact (Tomo/MRI if applicable).
6. Surgeon assessment: ease of detection; ease of device retrieval.
7. Participant satisfaction questionnaire: anxiety; convenience; pain; overall experience compared to expectation
8. Process improvement with implementation of same-day biopsy and SAVI SCOUT® placement.

[figure not shown]
4 Study Methods

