4.4 Study Assessments

	Consent*	Biopsy**	Surgery	Final Outcomes***
Patient Data				
Informed Consent	X			
Demographic information (age, height, weight, diagnosis)		X		
Neoadjuvant therapy (start and stop date)			X	
Device and Procedural Data				
Reflector insertion data (success, deployment within lesion or distance from lesion, depth of reflector, type of guidance used, number of reflectors used, type of lesion, reflector detection)		X		
Reflector detection (before incision or after incision)		X ⁱ	X	
Reflector retrieval (success, identification and retrieval duration)			X	
Operative time			X	
Adverse events (including device deficiencies)		X	X	

Scheduling Data				
Date of assessment		X		
Date of biopsy and insertion		X		
Date of surgery			X	
Satisfaction Assessments				
Radiologist assessment: ease of placement; ability to position reflector in desired location; scheduling flexibility; visibility on ultrasound/mammography; artifact (Tomo/MRI if applicable)				X ⁱⁱ
Surgeon assessment: ease of detection; ease of reflector removal				X ⁱⁱ
Participant satisfaction questionnaire			X ⁱⁱⁱ	
Pathology Report data				
Margins (positive; close <2mm; negative >2mm)				X
Re-excision required (after surgery)				X
Excised tissue volume/weight & specimen size				X

^{*}Performed prior to biopsy

^{**}Reflector insertion performed at time of biopsy

^{***}No additional participant visit; data recorded from pathology report

ⁱIf performed

ⁱⁱCollected once per clinician at completion of registry

ⁱⁱⁱWindow up to 2 weeks post-surgery (remote completion)

Identification of any number ranges for numeric endpoints along with their corresponding text descriptors.

- Continuous variables will be collected for: age, weight, height, operative time and adverse event rate, duration between events
- Categorical variables will be established for device success, procedural success, clinician assessment, participant satisfaction

5 Sample Size

No formal sample size calculation has been performed. Five hundred (500) participants will be included in this registry. This sample size has been selected to adequately support a multi-center experience reflective of the Canadian healthcare system and associated workflow.

Further, the Canadian Agency for Drugs and Technologies in Health (CADTH) assessed the evidence of STREAMLoc_Statistical Analysis Plan v1.0_30AUG2021

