7.5 Procedure Variables

Variable	Type of data/ unit
Lesion type	Categorical
Guidance type	Categorical
Lesion location	Categorical
Morphology classification	Categorical
Lesion size	Continuous/ mm
Lesion depth	Continuous/ cm
Reflector detection	Nominal
Deployment within lesion	Categorical
Distance from lesion	Continuous/ mm
Type of surgery	Categorical
Retrieval success	Nominal

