7.6 Treatment Variables

Variable	Type of data/ unit
Neoadjuvant therapy	Nominal
Duration of neoadjuvant therapy	Calculation (start- stop date)/ days
Number of visits for invasive procedures	Continuous

8 Utility Analyses

Number of visits for invasive procedures will be reported as: number, mean, standard deviation (SD), minimum, median and maximum values.

The primary endpoint will be compared to historical data using one-way analysis of variance.

9 Performance Analyses

Device and procedure success will be calculated as a percentage of the total number of cases, as well as the total number of reflectors used in the study.

10 Safety Analyses

- All reported adverse events will be categorized and described.
- Frequency and/ or percentage will be reported
- Adverse device effects (ADE) rates will be calculated separated
- ADEs will be sub-classified as appropriate
- Each participant will only be counted once and any repetitions will be ignored; the denominator will be the total population size
- Serious Adverse Events: A table of all anticipated and unanticipated serious adverse events, grouped by organ system, with number and frequency of such events in each arm/group of the clinical study. (See Adverse Events definition below).
- Other (Not Including Serious) Adverse Events: A table of anticipated and unanticipated events (not included in the serious adverse event table) that exceed a frequency threshold (for example, 5 %) within any arm of the clinical study, grouped by organ system, with number and frequency of such events in each arm/group of the clinical study.

11 Satisfaction Analyses

Clinician and participant satisfaction assessment data will be categorized and reported as frequency data.

12 Reporting Conventions

P-values ≥ 0.001 will be reported to 3 decimal places; p-values less than 0.001 will be reported as " <0.001 ". The mean, standard deviation, and any other statistics other than quantiles, will be reported to one decimal place greater than the original data. Quantiles, such as median, or minimum and maximum will use the same number of decimal places as the original data.

13 Summary of Changes to the Protocol and/or SAP

n/a

14 References

CADTH, 2019: CADTH rapid response report: summary with critical appraisal. Magnetic seed localization for soft tissue lesions in breast patients: Clinical effectiveness, cost- effectiveness, and guidelines.

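### SAP 7.1 ties insertion success to within-lesion deployment and has no row for detection, and SAP 9 also computes procedural success per reflector, so the reported success rates would not match the endpoints

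*SAP*

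**What the plan says.** Both documents (Protocol 4.2, SAP 3.2) define the endpoint as "Device success: percent successful localization, detection and retrieval".

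SAP 7.1 is the table that links each outcome to a case report form field. For the device it has two success rows: insertion, taken from "Inclusion CRF_Deployment within lesion", and retrieval, taken from "Surgery CRF_Reflector retrieval success". It has no detection row, and the SAP has no rule for combining the parts. Detection does appear elsewhere. SAP 7.5 lists "Reflector detection" as a nominal procedure variable, and the SAP 4.4 schedule collects it at surgery, and at biopsy if performed. Neither place ties it to device success.

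On placement, Protocol 3.2 describes delivery to a planned site "in close proximity or within the identified tissue lesion". Protocol 4.7 allows bracketing with more than one reflector, at least 25 mm apart. Its list of insertion data has a success item that is separate from within-lesion deployment and distance from the lesion.

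SAP 9 calculates both device success and procedure success as a percentage of cases, "as well as the total number of reflectors used in the study". SAP 6.2.1 and Protocol 5.3 place endpoint analysis on the per-protocol (PP) set, meaning reflector inserted and surgery done. SAP 6.2.2 adds an intention-to-treat (ITT) calculation for comparison.

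**The concern.** Performance is part of the secondary objective, and device success is the first secondary endpoint listed. Three features of the mapping pull the reported figures away from what the endpoints name.

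- **Insertion.** A field that asks whether the reflector lies within the lesion does not ask whether it was placed where intended. Correct placements next to the lesion could lower the rate.
- **Detection.** This is the function specific to the system. Protocol 2.2.3 and 3.1 say the reflector can also be located with imaging, and SAP 7.3 foresees back-up wires. Retrieval therefore does not prove that SCOUT detection worked.
- **Procedural success.** It rests on margins and re-excision, which are observed once per participant. A reflector denominator has no clear meaning for it.

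Two analysts following the SAP could report different rates from the same data.

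**Working it through.** The documents state no expected or target success rate, so there is no figure to reproduce. The check sets the endpoint beside the mapping and then sizes each gap.

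**Endpoint against mapping**

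| Part of endpoint | Source in SAP 7.1 | Item in Protocol 4.7 |
|---|---|---|
| Localization (taken here as insertion) | Within-lesion deployment | Insertion success, listed separately |
| Detection | None | Detection success, before or after incision |
| Retrieval | Retrieval success | Retrieval success |

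**Inputs from the plan:** 500 participants; at most 10% with a reflector but no surgery (Protocol 5.2, SAP 6.2.2). The PP set at that limit is 500 × (1 − 0.10) = 450. All other rates below are assumptions.

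**1. Insertion.** Let q be the share of placements that are permitted but outside the lesion. If only within-lesion deployment counts, the ceiling is 1 − q.

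- q = 5%, 10%, 20%, 30% gives 95%, 90%, 80%, 70%, even if every reflector went where intended.
- Bracketing contributes to q only when a reflector lies outside the lesion. The protocol does not say that it does. A lesion less than 25 mm across cannot contain two reflectors 25 mm apart, but the documents give no distribution of lesion size.

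**2. Detection.** Let d be the share of cases in which detection fails but the reflector is retrieved. A composite built only from the two mapped rows is too high by up to d.

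- d = 2% to 5% gives up to 2 to 5 points, or 450 × 0.02 = 9 to 450 × 0.05 = 22.5 participants.
- It is *up to* because some of these cases may already fail on insertion.

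**3. Procedural success per reflector.** Let b be the share of the 450 with two reflectors, the rest having one. Reflectors = 450 × (1 + b). At b = 10% this is 405 + 90 = 495. SAP 9 allows two readings.

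- *Successful participants over reflectors.* Ceiling = 1/(1 + b). For b = 5%, 10%, 20%: 450/472.5 = 95.2%, 450/495 = 90.9%, 450/540 = 83.3%.
- *Each reflector carries its participant's result.* Bracketed participants weigh 2b/(1 + b) instead of b. At b = 10% that is 90/495 = 18.2% instead of 45/450 = 10%. The rate moves by b(1 − b)/(1 + b) = 0.09/1.1 = 0.082 times the difference in success between bracketed and other participants. An assumed difference of 10 points shifts it by 0.8 points.

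**4. Scoring a case with several reflectors (device success).** Take b = 10% and suppose half of the 45 bracketed cases have one failed reflector, which is 22.5 failures.

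- Case fails if any reflector fails: (450 − 22.5)/450 = 95.0%.
- Case succeeds if at least one reflector succeeds: 450/450 = 100%.
- Per reflector: (495 − 22.5)/495 = 95.5%.

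The SAP does not choose between the two case rules.

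**The case against.** The strongest defence is that SAP 7.1 only points to fields and does not code them. It never says which value of the within-lesion field is a success, and SAP 7.5 lists that field as categorical with distance from the lesion beside it. The form itself is not among the documents. The endpoint can be read as three separate percentages, in which case no composite exists to be overstated. Detection is collected, and SAP 7 promises descriptive statistics for all endpoints. A per-case procedural rate is planned as well. The registry is descriptive, with no pass/fail criterion (Protocol 5.3), and this is one of eight secondary endpoints.

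Much of this stands. It makes the failure coding a natural reading and not a stated rule, and it makes the detection effect conditional on a composite. It does not supply a detection success definition, explain why the separate insertion success item is passed over, or give meaning to procedural success per reflector.

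A reader might also infer three stronger things that the documents do not support:

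- *Reflectors are the only denominator.* SAP 9 gives the per-case rate first; the reflector rate is additional.
- *The main retrieval rate is capped at 90% by participants who never have surgery.* Endpoint analysis is on the PP set, which excludes them, so its ceiling is 100%. The figure 450/500 = 90% applies only to the ITT comparison, at the upper limit of 10% without surgery and with equal numbers of reflectors per participant.
- *The rate cannot be compared with published device success.* That depends on definitions in sources outside these documents.

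**Conclusion.** The point holds as a defect in how SAP 7.1 and 9 turn the performance endpoints into variables. Three elements follow directly from the text: insertion success is sourced from within-lesion deployment although closer-than-within placement is not required and a success item exists; detection has no row; and procedural success is planned per reflector as well as per case.

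The sizes are conditional. Insertion success is capped at 95% to 70% if 5% to 30% of placements are permitted but outside the lesion and only within-lesion counts. A two-row composite is up to 2 to 5 points too high if 2% to 5% of cases are retrieved without detection. Procedural success per reflector is capped at 95.2% to 83.3%, or weights bracketed participants twice, if 5% to 20% of operated participants have two reflectors. The first two errors act in opposite directions, so their net effect cannot be signed in advance.

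The primary endpoint is not affected. The matter should be settled before the database is locked, because the reported rates depend on it.

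**What to change.** In SAP 7.1:

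- take insertion success from the insertion success item, and report within-lesion deployment and distance descriptively;
- add a detection success row from the surgery data, stating whether detection before and after incision both count;
- report insertion, detection and retrieval separately, and write down the rule for any composite.

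In SAP 9:

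- keep device success per case and per reflector, and say that both use the PP set already planned for endpoints;
- state how a case with several reflectors is scored when one succeeds and another fails;
- report procedural success per participant only.

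The cost is SAP wording. Protocol 4.7 already lists insertion, detection and retrieval success for collection. One check is needed first: that the form records detection and retrieval for each reflector, since the per-reflector rates depend on it.

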## AMENDMENT HISTORY

Protocol Version No.	Date Issued	Author(s) of Changes	Details of Changes Made
v1	5MAR2021	[name]	Original; pre-market registry
V2	16JUN2021	[name]	Change to post-market registry
V2.0 (US)	20SEP2022	[name] / [name]	Country specific amendment for US sites only
V3.0 (CA)	21FEB2023	[name]	Canadian specific amendment to include US sites, add physician adjudication, include additional device models

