### **4.2 Endpoints**

The primary endpoint is the number of patient visits to the breast center for invasive procedures from the time of biopsy to surgery. The primary endpoint will be compared to historical controls. It is expected that there will be a mean reduction of at least one (1) visit for invasive procedures.

The secondary endpoints are defined below:

1. Device success: percent successful localization, detection and retrieval.
2. Device safety: rate of device-related adverse events.
3. Procedural success: absence of close margins (<2mm), positive margins (tumor on ink) or requirement for re-excision.
4. Duration (days) from diagnosis to surgery and biopsy to surgery.
5. Radiologist assessment: ease of placement; ability to position reflector in desired location; scheduling flexibility; visibility on ultrasound/ mammography (immediate and late); artifact (Tomo/MRI if applicable).
6. Surgeon assessment: ease of detection; ease of device retrieval.
7. Participant satisfaction questionnaire: anxiety; convenience; pain; overall experience compared to expectation
8. Process improvement with implementation of same-day biopsy and SCOUT® Reflector placement.

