### 7.3 Reporting of safety related events

Adverse events and DD will be collected from the time the reflector is inserted into the participant (at biopsy) to the time the reflector is removed at surgery (Device Period) or until a study completion form is completed. Any AE in this period, either serious, non-serious, whether deemed device-related or not, must be reported to the Sponsor immediately after the investigator or coordinator has become aware of its occurrence. Reporting of an AE or DD to the Sponsor should take place within 24 hours upon becoming aware of the event, but not later than 3 calendar days. All AE (serious or non-serious) and DD will be documented in the eCRF. The AE/DD eCRF page should be submitted to the Sponsor within 24 hours even if all of the information is not available at the time of the initial contact. Sponsor contact for reporting: .

The investigator will evaluate (S)AEs with regard to causality and seriousness.

Reporting of serious incidents to the regulatory authorities will be reported per local regulations:

- Incident means any malfunction or deterioration in the characteristics and/or performance of the SCOUT® Surgical Guidance system, including use-error due to ergonomic features, any inadequacy in the information supplied by the manufacturer and any undesirable side-effect.
- Serious incident means any incident that directly or indirectly led, might have led or might lead to any of the following:
  - Death of a participant, user or other person,
  - Temporary or permanent serious deterioration of the participant's, user's or other person's state of health,
  - Serious public health threat;

Safety related events, which require preventive or corrective measurements intended to protect participants, may have to be reported to the local REBs/IRBs. The Sponsor will notify all other involved sites to report to their respective REBs/IRBs according to their requirements. The Sponsor will report any (S)ADEs and DD(s) to Health Canada and US FDA as required and within stipulated timelines.

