#### 7.3.1 Severity Definition

- Mild: Generally transient & not interfering with daily activities;
- Moderate: Sufficiently discomforting to interfere with usual activities;
- Severe: AE that prevents normal daily activities.

The investigator will document their assessment of the relationship of the AE to the device using the criteria outlined below.

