### **7.4 Independent Physician Adjudicator**

An independent Physician Adjudicator (IPA) will be responsible for review and adjudication of all serious and potentially device-related adverse events, at minimum. Other events may be reviewed as defined in the IPA Charter.

In order to enhance objectivity and reduce the potential for bias, the IPA shall be independent of the Sponsor as well as the investigational sites and investigators. The methodology for performing these responsibilities shall be developed and outlined in the IPA Charter. Operational provisions shall be established to minimize potential bias.

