## **8. Measures to Minimize Bias**

The following measures will be implemented to minimize the potential for bias in this single arm Registry:

- Sites are requested to screen and enroll consecutive subjects, as far as possible, and enrollment activities will be documented in a screening/enrollment log.
- Multiple sites will be included to ensure a representative sample of physicians performing the procedure and to provide a reasonable enrollment period.
- Site selection will be performed using predefined parameters to ensure Investigators are appropriately qualified to conduct registry.
- Site training will be performed to assure full understanding and engagement to comply with the study design and all protocol requirements.
- A sample of adverse events will be reviewed and assessed by an independent Physician.
- Any known or foreseeable factors that may compromise the outcome of the Registry or the interpretation of results are covered by the Inclusion and Exclusion criteria.
- Financial disclosures will be collected from all investigators to document any potential for bias or conflict of interest.

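### The SAP takes the device-related adverse event rate from a relatedness field on the AE form and makes no provision for the independent adjudication that protocol V3.0 added

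*SAP*

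**What the plan says.** The second secondary endpoint is "Device safety: rate of device-related adverse events" (protocol 4.2; SAP 3.2 has the same endpoint). The variable table in SAP 7.1 gives its source as "Adverse Event CRF_Device Related". The table lists no adjudicated variable. SAP 6.2.3 (safety population) and SAP 10 (safety analyses) do not mention adjudication and do not say who classifies an event as device-related.

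The protocol assigns causality to the site. Section 7.3: "The investigator will evaluate (S)AEs with regard to causality and seriousness". Section 7.3.1: "The investigator will document their assessment of the relationship of the AE to the device using the criteria outlined below".

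The amendment history describes V3.0 as "Canadian specific amendment to include US sites, add physician adjudication, include additional device models". Section 7.4 of that version states: "An independent Physician Adjudicator (IPA) will be responsible for review and adjudication of all serious and potentially device-related adverse events, at minimum". It gives objectivity and reduction of bias as the purpose, requires independence from the sponsor, sites and investigators, and leaves the method and any further events to an IPA Charter. Section 8, among the measures against bias, states: "A sample of adverse events will be reviewed and assessed by an independent Physician".

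Protocol 5.3 places the full analysis in the SAP, to be specified in the final report. The SAP is v1.0 of 30AUG2021, nearly 18 months older than protocol V3.0, and its section 13 records no changes.

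**The concern.** The registry is single-arm and unblinded. Clinicians at the participating sites place and retrieve the reflector. Several of the event types in protocol 7.2, such as inaccurate deployment, inaccurate location detection and tissue or vascular trauma, can reflect operator technique as well as the device. Relatedness is therefore a judgement on which an independent view has value, and the sponsor added one for that reason.

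The analysis plan was not updated to use it. A statistician who follows SAP 7.1 literally counts whatever stands in the form's relatedness field. If the adjudicator disagrees with the site, no rule says which answer is counted. If the choice is left to the final report, it can be made after the data are seen, and under protocol 5.3 the sponsor does both the data management and the analysis.

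Two smaller points concern scope. Sections 7.4 and 8 of the protocol describe it differently. In addition, the guaranteed review in 7.4 reaches a non-serious event only if someone regards it as potentially device-related, and the natural reading is that the investigator's grade decides this.

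**Working it through.** The plan gives no expected device-related event rate and no sample-size calculation, so there is no stated figure to reproduce. The check is a comparison of texts, followed by an illustration of size.

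**Source of the endpoint**

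1. SAP 7.1 names one field on the AE form.
2. Protocol 7.3 and 7.3.1 make the investigator the assessor of causality and of relationship to the device.
3. From 1 and 2, the field most naturally holds the investigator's assessment. This is an inference, because the SAP names no assessor.
4. Adjudication came in with V3.0 (21FEB2023). SAP v1.0 (30AUG2021) could not have provided for it, and no later SAP version is among the documents.
5. Neither document contains a rule of precedence.

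**Scope of adjudication**

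| Protocol section | Events reviewed |
|---|---|
| 7.4 | All serious and all potentially device-related events, as a minimum; others per the Charter |
| 8 | A sample of adverse events |

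The two can be reconciled only if a complete, defined subset is called a sample. The wording is inconsistent and could lead to different workloads.

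**Direction of possible reclassification**

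Assume that the investigator's grade decides what is potentially device-related, and that a grade of possibly related counts towards the rate. Every event counted as device-related is then guaranteed review and can be removed. An event graded unrelated is guaranteed review only if it is serious. For non-serious events, guaranteed adjudication could therefore remove cases from the rate but not add them.

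**Size (illustration)**

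Inputs:
- N = 500 (protocol 5.1).
- Each participant is counted once, over the total population (SAP 10).
- The upper ends of the annual complaint rates in protocol 9.3 are 0.02% (reaction to materials), 0.08% (tissue/vascular trauma), 0.48% (inaccurate location detection), 0.22% (inaccurate deployment) and 0.02% (migration).

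Arithmetic:
- One participant reclassified: 1/500 = 0.2 percentage points, provided that the participant has no other device-related event.
- Sum of upper ends: 0.02 + 0.08 + 0.48 + 0.22 + 0.02 = 0.82%.
- Expected in 500: 500 × 0.0082 = 4.1, about 4 participants.

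Both documents specify a one-sided 95% interval but no method. Assuming the exact (Clopper-Pearson) method, the upper bound is the 0.95 quantile of Beta(x + 1, 500 − x):

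| Participants x | Rate x/500 | One-sided 95% upper bound |
|---|---|---|
| 2 | 0.4% | 1.25% |
| 4 | 0.8% | 1.82% |
| 6 | 1.2% | 2.35% |

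Starting from 4, removing two halves the rate (0.8% to 0.4%). Adding two raises it by half (0.8% to 1.2%).

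**The case against.** **The documents are silent; they do not exclude adjudicated results.** A reader might infer that adjudication cannot change the reported rate. The documents do not support that. The SAP names a form field and not an assessor. The IPA Charter, which is not among the documents, could set precedence or have the field updated, and protocol 5.3 lets the final report specify the analysis. This objection stands as a limit on the claim: no provision in the SAP as written carries adjudication into the endpoint. It does not close the gap, because 7.4 gives the Charter the adjudication method, while 5.3 gives the analysis to the SAP.

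**Sections 7.4 and 8 need not contradict each other.** A reader might infer that one section says all events and the other a sample. Section 7.4 does not say all events. It covers serious and potentially device-related ones at minimum, and section 8 may be referring loosely to that subset. It is an inconsistency to align, and it is not the cause of the missing rule.

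**The gatekeeping point is inferred.** Section 7.4 does not say who decides what is potentially device-related, 7.3 sends every event to the sponsor whatever its grade, and the Charter may add events. An event such as migration is hard to regard as anything but potentially device-related. This is fair, and it is the reason to state the rule explicitly.

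**The size is uncertain.** Annual complaint rates are not per-participant event rates, so they give only an order of magnitude. A larger effect might be inferred from the infection rates of 1.56–4.61% in protocol 9.3. Those belong to other localization systems, and the same entry reports no infections from the reflector, so they are not used here.

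**Little depends on the result.** Protocol 5.3 says that the registry is not hypothesis driven and has no pass/fail criteria. A shift of a few tenths of a point crosses no threshold. This stands and limits the severity.

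**Conclusion.** The point holds in a limited form. SAP v1.0 derives the device-related event rate from a field that is most naturally the investigator's assessment. It makes no provision for the adjudicated classification that protocol V3.0 introduced, and nothing says which prevails. The scope wording in protocol 7.4 and 8 is a separate inconsistency.

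The size is 0.2 percentage points per reclassified participant. With a true count near 4 in 500, two reclassifications change the rate by half in either direction. The count near 4 rests on treating annual complaint rates as a rough guide, and the two reclassifications are assumed: the documents give no basis for a disagreement rate. That the form field is the investigator's is an inference from protocol 7.3 and 7.3.1, and the unseen Charter may already settle part of this.

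Severity is modest. The endpoint is secondary and descriptive, but the remedy is cheap and is best made before database lock.

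**What to change.** 1. **SAP 7.1 and 10.** Use adjudicated relatedness as the source of the device-safety endpoint where an event was adjudicated, and the investigator's assessment otherwise. State that the adjudicated decision prevails on disagreement.
2. **SAP 10.** Report the investigator-assessed rate as a sensitivity result, with a table of disagreements by event type and direction.
3. **Protocol 8.** Replace the reference to a sample with the scope in 7.4.
4. **Protocol 7.4.** State that potentially device-related includes the six event types named in 7.2, whatever causality grade the investigator gives, so that review can add as well as remove non-serious events.
5. **IPA Charter.** Check that it agrees with these changes.

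The cost is a SAP update, small edits to two protocol sections and a few more events for an adjudicator who is already provided for. The reported rate may be slightly higher. A less extensive alternative is to name the source, state which assessment prevails and report both rates. That would close the main gap but leave the one-directional review of non-serious events.
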